9.5. Study Size

The planned analyses do not involve hypothesis testing and sample size calculations are not applicable. However, we examined the precision of PCV13 vaccine effectiveness for IPD and all-cause pneumonia among people living with HIV at 36 months and 97 months (which was the maximum follow-up time available from feasibility assessments) after index (Table 2 and Table 3). Komodo Health provided the following information for the precision estimates:

- 175,000 individuals had ≥ 1 inpatient or ≥ 2 outpatient HIV ICD-9-CM or ICD-10-CM code diagnosis codes between January 1, 2014 and December 31, 2021
- 56,000 (32%) of these individuals received PCV13 after their first HIV diagnosis code

The following assumptions regarding incidence and PCV13 VE for IPD and all-cause pneumonia were used:

- IPD incidence among PLWH is 183 cases per 100,000 population [28]
- All-cause pneumonia incidence among PLWH is 5,487 cases per 100,000 population
- VE for IPD due to any serotype ranges from 7.5% to 22.5%
 - Published VE estimates for vaccine type IPD range from 25% to 75% [20]. Because one-third of the adult IPD burden is considered PCV13 type [29], we multiplied this range by 30% to arrive at 7.5% to 22.5%
- VE for all-cause pneumonia ranges from 5% to 15% [30]
- Annual censoring of individuals due to loss to follow-up or death may range between 4% or 10%

Survival and censoring times were simulated assuming exponential distributions. Vaccination status was modelled as a time-varying covariate [31]. Hazard ratios were assumed as $1 - (VE/100)$. Simulations were run 100 to 200 times per scenario. Cox regression models were run on each simulated dataset to estimate the 95% confidence

PFIZER CONFIDENTIAL

intervals (CI) for the log HRs. Means were generated and exponentiated to obtain the 95% CIs for the VEs using $(1 - HR) \times 100$ and used to describe VE precision.

Table 2. Precision of PCV13 vaccine effectiveness estimates for invasive pneumococcal disease

Hypothesized Vaccine Effectiveness (%)	36 months of follow-up			97 months of follow-up		
	Lower 95% confidence interval estimate	Upper 95% confidence interval estimate	Total number of events	Lower 95% confidence interval estimate	Upper 95% confidence interval estimate	Total number of events
Scenario #1 – 4% annual censoring						
7.5	-12	25	837	-5	19	1492
22.5	3	37	817	11	33	1452
Scenario #2 – 10% annual censoring						
7.5	-15	25	766	-6	21	1272
22.5	2	38	752	9	33	1224

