Several stratified analyses will be conducted. PPSV23 is recommended for PLWH and feasibility data provided by Komodo suggest that one in four PWLH who received PCV13 during 2014-2015 also received PPSV23 within two years. Rather than censor or exclude

individuals who receive PPSV23, we will calculate PCV13 VE among PWLH who have/have not received PPSV23 before and during the study period.

Feasibility assessments from Komodo indicate that approximately 25% of PWLH have at least one CD4 cell count or percentage laboratory result available. Therefore, we will calculate PCV13 VE among the subset of PWLH who have a CD4 cell count during the baseline period or follow-up, and potentially stratify by CD4 category using each patient's lowest value during the study.

Additional VE stratifications by ART adherence during follow-up, year of HIV diagnosis, and age will be assessed for feasibility as well, as these affect patients' immune status and immune reconstitution. Due to possible waning of the VE and different lengths of follow-up by index year, VE stratification by year of HIV diagnosis will be restricted to the first 3 years of follow-up.

A sensitivity analysis will also be conducted. In this analysis, causes of pneumonia that are characteristic of HIV, for example pneumonia due to cytomegalovirus, mycobacteria, and fungi, will be excluded from our definition of all-cause pneumonia.

Residual confounding of our VE estimates due to inadequate control for health care seeking behavior and immune status in our analyses will be explored. To do so, we will employ a negative control exposure and a negative control outcome. Potential negative control exposures include vaccinations that are recommended for PLWH but would not be expected to have any protective effect against the pneumonia outcomes of interest. If residual confounding does not exist, the negative control vaccine would not have an effect on the pneumonia outcomes. However, if the analysis demonstrates that the negative control vaccine protects against these outcomes, this suggests the presence of residual confounding.

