### 5.2.3. Subgroups and Stratification

*Several stratified analyses will be conducted. PPSV23 is recommended for PLWH and feasibility data provided by Komodo suggest that one in four PWLH who received PCV13 during 2014-2015 also received PPSV23 within two years. Rather than censor or exclude individuals who receive PPSV23, we will calculate PCV13 VE among PWLH who have/have not received PPSV23 before and during the study period. The analysis may also be stratified by the number of PPSV23 doses, e.g. 0, 1, 2+.*

*Feasibility assessments from Komodo indicate that approximately 25% of PWLH have at least one CD4 cell count or percentage laboratory result available. Therefore, we will calculate PCV13 VE among the subset of PWLH who have a CD4 cell count during the baseline period or follow-up, and potentially stratify by CD4 category using the patient's lowest value during the study.*

*Additional VE stratifications by ART adherence during follow-up, year of HIV diagnosis, and age will be assessed for feasibility as well, as these affect patients' immune status and immune reconstitution. Due to possible waning of the VE and different lengths of follow-up by index year, VE stratification by year of HIV diagnosis will be restricted to the first 3 years of follow-up (0 to 1079 days).*

The above subgroup analyses will be conducted if there are sufficient numbers of patients/events to maintain patient de-identification (Section 5.8.3) and where the 95% confidence intervals (CI) for the VE estimates can be expected to exclude zero in the best case scenarios for the analyses, i.e. the highest expected VE estimate, the lowest expected censoring rate and at the maximum follow-up time. Table 5.1 provides precision estimates for IPD and all-cause pneumonia under different numbers of individuals available for the analysis. The following assumptions were used for the estimates:

- 32% of individuals received PCV13
- IPD incidence among PLWH is 183 cases per 100,000 population [1]
- All-cause pneumonia incidence among PLWH is 5,487 cases per 100,000 population
- VE for IPD due to any serotype is 22.5% [2, 3]
- VE for all-cause pneumonia is 15% [4]

- Annual censoring of individuals due to loss to follow-up or death is 4%
- Up to 97 months of follow-up

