Survival and censoring times were simulated assuming exponential distributions. Vaccination status was modelled as a time-varying covariate [5]. Hazard ratios were assumed as 1-(VE/100). Simulations were run 100 to 200 times per scenario. Cox regression models were run on each simulated dataset to estimate the 95% CIs for the log HRs. Means were generated and exponentiated to obtain the 95% CIs for the VEs using  $(1 - HR) \times 100$  and used to describe VE precision.

**Table 5.1 Precision of PCV13 Vaccine Effectiveness Estimates for Invasive Pneumococcal Disease and All-Cause Pneumonia Subgroup Analyses**

Number of individuals	IPD VE: 22.5%		All-cause pneumonia VE: 15%	
	Lower 95% confidence interval estimate	Upper 95% confidence interval estimate	Lower 95% confidence interval estimate	Upper 95% confidence interval estimate
87,000 (N/2)	6%	37%	11%	18%
58,000 (N/3)	1%	40%	11%	19%
43,000 (N/4)	-5%	41%	10%	20%
35,000 (N/5)	-6%	44%	9%	20%
29,000 (N/6)	-9%	46%	9%	20%
22,000 (N/8)	-16%	49%	8%	21%

Table 5.1 shows that, under the current assumptions, 95% CIs for the IPD VE would still be expected to exclude 0% in subgroups with 58,000 individuals. For all-cause pneumonia the 95% CIs for the VE would still be expected to exclude 0 in subgroups with fewer than 22,000 individuals. Therefore, the study should have sufficient precision to address the study the objectives in several of the planned subgroups.

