## 5.8. Statistical Methodology and Analyses

### 5.8.1. General Considerations

Descriptive statistics will be used to summarize variables. For categorical variables, the frequency and percentage of patients in each category will be presented. Percentages will be based on the total number of relevant patients, including those with ‘unknown’ or missing values. For continuous variables, data will be presented as means, standard deviations, medians, 25th and 75th percentiles, minimums and maximums. Continuous variables may be additionally categorized and analyzed as categorical variables.

No statistical hypotheses are specified and there will be no correction for multiple comparisons.

Time in years between two dates will be calculated as (end date – start date) + 1, divided by 365.25, unless otherwise specified.

All data analysis will be conducted in R, version 4.1.3 or later (R Foundation for Statistical Computing, Vienna, Austria).

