#### 5.8.11. Analysis of Study Objectives

Crude HRs for PCV13 vaccination and the corresponding VE percentages will be presented together with 95% CIs for each study outcome overall and again during specific time periods (0-3, 3-5, 5-7 years). This will be done for first events and again including recurrent events. Analysis will be repeated using Cox-MSM after applying IPT and the IPT\*IPC weights.

The above analysis will be repeated by the subgroups stated in Section **Error! Reference source not found..**

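### Subgroup vaccine effectiveness (VE) is estimated stratum by stratum with no between-stratum comparison and no exploratory label; IPD strata with equal VE would often seem to differ

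*SAP*

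**What the plan says.** SAP 5.2.3 and Protocol 9.7 stratify VE by PPSV23 receipt and, where feasible, by CD4 category, ART adherence, year of HIV diagnosis and age. The last three are justified "as these affect patients' immune status and immune reconstitution". SAP 5.2.3 runs a subgroup if counts are large enough for de-identification and "where the 95% confidence intervals (CI) for the VE estimates can be expected to exclude zero in the best case scenarios for the analyses". Table 5.1 then gives expected CIs by stratum size, assuming "VE for IPD due to any serotype is 22.5"% and "VE for all-cause pneumonia is 15"%, and the section ends: "Therefore, the study should have sufficient precision to address the study the objectives in several of the planned subgroups".

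For the analysis itself, SAP 5.8.11 says "The above analysis will be repeated by the subgroups stated in Section", followed by a broken cross-reference whose evident target is 5.2.3. SAP 5.8.4 regenerates the weights within each subgroup. The only interaction in either document is vaccination by time period, in the example code of SAP 7.2.5. No ratio of stratum HRs, interaction term or heterogeneity statistic by subgroup appears. SAP 5.8.1 adds: "No statistical hypotheses are specified and there will be no correction for multiple comparisons".

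**The concern.** Choosing strata because they affect immune status raises the question of whether VE differs between them, and the plan produces nothing that answers it. It gives one VE and CI per stratum and one benchmark, exclusion of zero. A reader who sees one CI exclude zero and its neighbour include it will tend to conclude that PCV13 works in one group of people with HIV and not in the other. That pattern is not evidence of a difference. With strata near the smallest size the SAP admits for IPD, it is common even when VE is identical.

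The opposite error is also open. For all-cause pneumonia, where every stratum may exclude zero, a real difference in VE would go unexamined.

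**Working it through.** **Inputs.** SAP Table 5.1: IPD CI 6% to 37% at 87,000 and 1% to 40% at 58,000 (VE 22.5%); all-cause pneumonia 11% to 18% at 87,000 and 8% to 21% at 22,000 (VE 15%). Protocol Table 2 (4% censoring, 97 months): IPD 11% to 33% with 1,452 events for the whole cohort of 175,000. Protocol Table 3: 38,848 pneumonia events at VE 5%.

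**Reproducing Table 5.1.** SE of log HR = [ln(1 − lower) − ln(1 − upper)] / 3.92. For the whole cohort this is (−0.1165 + 0.4005)/3.92 = 0.0724. Dividing by √(1/2) gives 0.1024 and a CI of 5.3% to 36.6%, against 6% to 37% stated. Dividing by √(1/3) gives 0.1255 and 0.9% to 39.4%, against 1% to 40%. The table is sound.

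**Chance that one IPD stratum excludes zero.** P = Φ(−ln 0.775/SE − 1.96), with −ln 0.775 = 0.2549.
- 87,000: SE = (−0.0619 + 0.4620)/3.92 = 0.102; P = Φ(2.50 − 1.96) = 0.70.
- 58,000: SE = (−0.0101 + 0.5108)/3.92 = 0.128; P = Φ(2.00 − 1.96) = 0.51.
- About 117,000 (two thirds): SE = 0.0724/√(2/3) = 0.0887; P = 0.82. The matching third, scaled the same way, has P = 0.53.

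**Chance that strata with the same VE disagree.** For k equal independent strata this is 1 − P^k − (1 − P)^k; for two unequal strata, P1(1 − P2) + P2(1 − P1).

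| IPD, true VE 22.5% in every stratum | Disagree |
|---|---|
| Two of 87,000 | 2 × 0.70 × 0.30 = 42% |
| About 117,000 and 58,000 | 0.82 × 0.47 + 0.53 × 0.18 = 48% |
| Three of 58,000 | 1 − 0.51³ − 0.49³ = 75% |

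Three strata of 58,000 use 174,000 of the 175,000. With 58,000 the smallest tabulated size that passes the rule, a three-way split passes throughout only if its strata are nearly equal.

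At the protocol's lower IPD figure ("VE for IPD due to any serotype ranges from 7.5% to 22.5"%), disagreement falls to 21% (two strata) and 25% (three), because most strata then include zero.

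**All-cause pneumonia.** At VE 15% the SE at 87,000 is 0.0209 and P is practically 1. Disagreement is under 0.1% for two to four equal strata of the whole cohort, and about 3% for two strata of 22,000 (SE 0.0389, P = 0.987). At VE 5%, use SE = 1/√(events × q), with q = 1/(1,452 × 0.0724²) = 0.131:
- Two strata of 19,424 events: SE 0.0198, P = Φ(2.59 − 1.96) = 0.74, disagreement 39%.
- Three strata of 12,949 events: SE 0.0243, P = 0.56, disagreement 74%.

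**What a direct comparison would give.** SE of the difference in log HR for two equal strata = √2 × SE.
- IPD, two of 87,000: 0.144. The 95% CI multiplies the ratio of HRs by 0.75 to 1.33, with 80% power only for a ratio of exp(−2.80 × 0.144) = 0.67 or more extreme.
- All-cause pneumonia, two of 87,000: 0.0296. The factor is 0.94 to 1.06, and the detectable ratio is 0.92.

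**The case against.** The SAP does not say that subgroup results will be read against zero. Exclusion of zero decides whether a subgroup is run, the study states no hypotheses, and the only written reading of that kind concerns the negative controls (SAP 5.8.12). No listed objective concerns effect modification, PPSV23 stratification is offered as an alternative to censoring or excluding recipients, and most subgroups are conditional on feasibility. All of this stands. A reader might infer that the plan prescribes a misreading; it does not. What remains is that it offers no other benchmark, no comparison and no caution. An estimation study can report a ratio of HRs with a CI without testing anything.

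Two stronger readings also fail. One is that equal strata will usually look different. For two-level IPD splits that pass the rule, each stratum has at least about a 50% chance of excluding zero, so disagreement cannot exceed about 50%; for all-cause pneumonia at VE 15% it is negligible. The other is to count some 14 strata per outcome (PPSV23 2, CD4 3, ART 2, year 4, age 3) and quote a family-wise error of 1 − 0.95^14 = 0.51. The SAP's rule removes many of these for IPD. The whole CD4 subset is about 25% of 175,000 = 43,750, and Table 5.1 gives a lower limit of −5% at 43,000. Year strata are confined to three years, where the full-cohort CI is 3% to 37% (SE 0.110), so half the cohort (SE 0.156) would have a lower limit near −5%.

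It is also fair that a direct comparison has a 5% error rate per factor, about 1 − 0.95^5 = 23% over five independent factors, and that IPD comparisons will be weak. These points limit the remedy without removing the need for it.

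**Conclusion.** The point holds as a gap in reporting, of minor severity. The plan estimates VE by stratum, never compares strata and does not label the results exploratory. Under the SAP's best-case assumptions, IPD strata with identical VE would disagree on excluding zero in about 42% to 48% of two-level splits and 75% of three equal strata. All-cause pneumonia is little affected at VE 15% (0 to 3%) but would be near VE 5% (39% and 74%).

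The figures assume each patient falls in one stratum of a factor, so that estimates are independent; the SAP's 4% censoring and 97 months; and no loss of precision from weighting, which would widen the CIs. The documents do not give the actual sizes of the PPSV23, ART or age strata, so the splits are illustrations. The overall primary VE estimates are not touched.

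**What to change.** In SAP 5.8.11, for each subgroup factor and outcome that is run:
1. Report the ratio of stratum HRs with its 95% CI, from the stratum-specific weighted log HRs and robust SEs. With three or more strata, compare each with a reference; Cochran's Q is optional.
2. State that any claim that VE differs by subgroup rests on this comparison, not on which stratum's CI excludes zero.
3. Label subgroup VEs exploratory, and reword the closing sentence of SAP 5.2.3 so that it claims only enough precision *to describe VE* in several of the subgroups.
4. Where strata use information from after the index date (ART adherence over follow-up, lowest CD4 during the study, PPSV23 received during the study), present the comparison as descriptive only.

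The cost is some SAP wording and one line of arithmetic per factor from estimates already planned; nothing needs refitting. The drawback is that IPD ratios will be imprecise, and the CIs will show it.

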### 5.3. Variables

#### 5.3.1. Effectiveness Endpoints

The outcomes of interest for the primary and secondary objectives are listed in Table 5.2.

Episodes separated by at least 90 days will be considered independent events. For claims that include pneumonia that are separated by <90 days, those claims will be collapsed into a single episode with a date of the initial diagnosis.

**Table 5.2 Outcomes of Interest**

Outcome Type	Outcome	Definition
Primary outcomes	IPD	ICD-9-CM or ICD-10-CM codes listed in Appendix Table 7.4
	Pneumococcal pneumonia	ICD-9-CM or ICD-10-CM codes listed in Appendix Table 7.4
	All-cause pneumonia	ICD-9-CM or ICD-10-CM codes listed in Appendix Table 7.4
Secondary outcomes	Pneumococcal pneumonia or pneumonia with unspecified causes	ICD-9-CM or ICD-10-CM codes listed in Appendix Table 7.5
	Pneumonia with unspecified causes	ICD-9-CM or ICD-10-CM codes listed in Appendix Table 7.5
Sensitivity analysis outcome	All-cause pneumonia not associated with HIV	ICD-9-CM or ICD-10-CM codes listed in Appendix Table 7.6

For combination diagnosis codes, (e.g., bacteremia + pneumococcus) for diagnoses in an inpatient setting patients must have all codes within the same admission. The latest date of the combination of diagnoses will be used as the diagnosis date. For diagnoses in an outpatient setting patients must have all codes within the same date.

### 5.3.2. Covariates

The list of demographic and clinical characteristics considered for descriptive reporting, subgroups and inclusion as covariates in models for generating the propensity scores are provided in Table 5.3. The Komodo Health database will be source of all variables.

Patients will be considered to have a comorbidity or hospitalization during baseline if there was evidence of a diagnosis at any time during the baseline period. Evidence of comorbidities or hospitalization during follow-up will be considered as new diagnoses. Once diagnosed, patients will be considered diagnosed for the remainder of their follow-up. ART adherence during baseline and follow-up will be updated every 6 months (180 days) based on the data collected in that previous timeframe. For baseline annual physical exam and annual influenza vaccine, patients will be considered adherent (coded as 'Yes') if there was evidence of these events at any time during the baseline period. During the follow-up, patients will be considered adherent up to 365 days after the last event date.

For annual CD4 and viral load laboratory tests during baseline and follow-up, patients will be coded as 'Yes' up to 365 days after the last event date. For respiratory virus season during follow-up, patients will be coded as 'Yes' if the observation time is in October, November, December, January, February, March or April.

The baseline period for the assessment of covariates is the six months prior to the index date, i.e., no data prior to six months will be included.

Covariates used at baseline only will be considered time-fixed confounders. Covariates additionally or only used during follow-up will be considered time-varying confounders.

Categories may be collapsed, or covariates may be excluded from the propensity scores if models fail to converge.

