9.2.1. Inclusion Criteria

To be eligible for the vaccine effectiveness study, individuals must meet the following criteria:

1. HIV infection defined as at least one inpatient International Classification of Diseases, Ninth Revision, Clinical Modification (ICD-9-CM) or International Classification of Diseases, Tenth Revision, Clinical Modification (ICD-10-CM) code related to HIV (Appendix Table 1) or ≥ 2 outpatient ICD-9-CM or ICD-10-CM codes related to HIV at least 30 days, but no more than 730 days apart, during January 1, 2014 and December 31, 2021

AND

2. At least 18 years of age at the time of the first recording of HIV-related ICD-9-CM or ICD-10-CM code

PFIZER CONFIDENTIAL

CT24-WI-GL02-RF02 5.0 Non-Interventional Study Protocol Template For Secondary Data Collection Study 01-Aug-2023

AND

[figure not shown]
3. At least six months of continuous enrollment in medical and pharmacy plans after the first HIV-related ICD-9-CM or ICD-10-CM code between January 1, 2014 and December 31, 2021. A gap of 30 days or less in enrollment will be allowed during this six month period.

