9.7. Data Analysis

Cox proportional hazards models will be used to estimate the hazard ratio (HR) for each outcome comparing vaccinated PLWH with unvaccinated (no PCV13) PLWH. To explore potential changes in VE over time, HRs will also be generated during specific time periods (0-3, 3-5, 5-7 years of follow-up) using piecewise Cox regression models, if there is adequate sample size. All models will be adjusted for time-fixed and time-varying covariates of interest using inverse probability of treatment weighting. The time-fixed covariates of interest include sex, age, payor, SVI, previous pneumonia infection, and hospitalization and will be measured during the baseline period. The time-varying covariates include risk factors for pneumonia (alcoholism, asplenia, asthma, chronic heart disease, kidney, liver, and lung diseases, cigarette smoking, diabetes, immunosuppressive conditions and medications, and sickle cell disease), annual physical exams, annual influenza vaccine, hospitalization, opportunistic infections, ART adherence, annual CD4 and viral load laboratory tests, and an indicator for respiratory virus season.

VE will be calculated as 1 minus the estimated HR for each outcome.

We will conduct two sets of analyses for each outcome. In the first set, we will examine the first event for each outcome and in the second set, all recurrent outcome events during follow-up will be included. In the first set of analyses, unvaccinated (no PCV13) PLWH will be followed from index date until the earliest occurrence of the following: outcome, PCV13 vaccination, death, end of health plan enrollment, or end of study period, and vaccinated PLWH will be followed from 14 days after vaccination date, or index date if vaccinated during the baseline period, until the earliest occurrence of outcome, death, end of health plan enrollment, or end of study period. In the second set of analyses unvaccinated (no PCV13) PLWH will be followed from index date until the earliest occurrence of PCV13 vaccination, death, end of health plan enrollment or end of study period and vaccinated PLWH will be followed from 14 days after vaccination date, or index date if vaccinated during the baseline period, until earliest occurrence of death, end of health plan enrollment, or end of study period.

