Asthma	ICD-9-CM or ICD-10-CM codes listed in Protocol Annex Table 1.3 Yes, No	Descriptive, covariate	Baseline and follow-up
Diabetes mellitus	ICD-9-CM or ICD-10-CM codes listed in Protocol Annex Table 1.9 Yes, No	Descriptive, covariate	Baseline and follow-up
Generalized malignancy	CPT/HCPCS, ICD-10-PCS, ICD-9-PCS, ICD-9-CM or ICD-10-CM codes listed in Annex Table 1.10	Descriptive, covariate	Baseline and follow-up
Immunosuppressive medications	PLWH will be considered on immunosuppressive medications if: 1) ≥1 NDC, HCPCS, or ICD-10-PCS code in Appendix Table 7.7	Descriptive, covariate	Baseline and follow-up

	2) ≥ 1 NDC (using oral only) in Appendix Table 7.7 where the daily dose is ≥ 20mg or prednisone or prednisone equivalent for a duration of ≥14 consecutive days Yes, No		
Leukemia	ICD-9-CM or ICD-10-CM codes listed in Protocol Annex Table 1.12	Descriptive, covariate	Baseline and follow-up
Multiple myeloma	ICD-9-CM or ICD-10-CM codes listed in Annex Table 1.13	Descriptive, covariate	Baseline and follow-up
Nephrotic syndrome	ICD-9-CM or ICD-10-CM codes listed in Protocol Annex Table 1.14 Yes, No	Descriptive, covariate	Baseline and follow-up
Non-Hodgkin's lymphoma	ICD-9-CM or ICD-10-CM codes listed in Protocol Annex Table 1.15	Descriptive, covariate	Baseline and follow-up
Organ transplant	CPT/HCPCS, ICD-10-PCS, ICD-9-PCS, ICD-9-CM or ICD-10-CM codes listed in Protocol Annex Table 1.16	Descriptive, covariate	Baseline and follow-up
Sickle cell disease or other hemoglobinopathies	ICD-9-CM or ICD-10-CM codes listed in Protocol Annex Table 1.17 Yes, No	Descriptive, covariate	Baseline and follow-up
Hepatitis B	ICD-9-CM or ICD-10-CM codes listed in Protocol Annex Table 2.1 Yes, No	Descriptive, covariate	Baseline and follow-up
Hepatitis C	ICD-9-CM or ICD-10-CM codes listed in Protocol Annex Table 2.2 Yes, No	Descriptive, covariate	Baseline and follow-up
Cigarette smoking	ICD-9-CM or ICD-10-CM codes listed in Protocol Annex Table 1.7 Yes, No	Descriptive, covariate	Baseline and follow-up
Annual physical exam	CPT/HCPCS codes listed in Protocol Annex Table 3.1 Yes, No	Descriptive, covariate	Baseline and follow-up
Annual influenza vaccine	CPT/HCPCS, ICD-10-PCS, ICD-9-PCS, or NDC codes listed in Appendix Table 7.8 Yes, No	Descriptive, covariate	Baseline and follow-up
Any pneumonia infection	ICD-9-CM or ICD-10-CM codes listed in Appendix Table 7.4 Yes, No	Descriptive, covariate	Baseline

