Any hospitalization	Evidence of inpatient claim(s) Yes, No	Descriptive, covariate	Baseline and follow-up
Hodgkin's lymphoma	ICD-9-CM or ICD-10-CM codes listed in Protocol Annex 1.11 Yes, No	Descriptive, covariate	Baseline and follow-up
Opportunistic infections	ICD-9-CM or ICD-10-CM codes listed in Protocol Annex Table 14	Descriptive, covariate	Baseline and follow-up

	Yes, No  Note: In the analysis of all-cause pneumonia, pneumocystis jirovecii pneumonia codes are excluded from the follow-up. In the analysis of candidiasis negative control outcomes, candidiasis infection codes are excluded from the follow-up.		
Antiretroviral treatment (ART) adherence	ART use will be identified by NDC codes listed in Appendix Table 7.2  Adherence will be measured as 'Proportion of days covered = (Number of days covered by any ART, excluding ritonavir and cobicistat) ÷ (total days)*100'[8] every six months  Individuals with >80% of days covered will be classified as 'adherent' and individuals with ≤80% of days covered will be classified as 'non-adherent'[8]. Individuals without ART information will be classified as Missing. As a subgroup, ART adherence will be calculated using the information over the entire follow-up.	Descriptive, covariate, subgroup	Baseline and follow-up
CD4 cell count	Categorized as <200, 200-499, ≥500 cells/mm 	Descriptive, subgroup	Baseline and follow-up
PPSV23 vaccination	NDC and CPT codes listed in Appendix Table 7.9  Yes, No. 0, 1, 2+ doses	Descriptive, subgroup	Before first HIV diagnosis, baseline and follow-up
Annual CD4 laboratory test	CD4 laboratory tests will be identified by CPT codes listed in Appendix Table 7.11  Individuals who have at least one CD4 laboratory test performed during each year of follow-up Yes, No	Covariate	Baseline and follow-up
Annual viral load laboratory test	Viral load laboratory tests will be identified by CPT codes listed in Appendix Table 7.12  Individuals who have at least one viral load laboratory test performed during each year of follow-up Yes, No	Covariate	Baseline and follow-up

Respiratory virus season	Respiratory virus season occurs between October 1 and April 30 Yes, No	Covariate	Follow-up
--------------------------	---	-----------	-----------

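### Hospitalization is coded once-yes-always-yes, so the time-varying weights adjust for a first admission but not for recent or repeated illness

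*SAP*

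**What the plan says.** SAP 5.3.2 sets the baseline value, looking back over the six months before index: "Patients will be considered to have a comorbidity or hospitalization during baseline if there was evidence of a diagnosis at any time during the baseline". For follow-up it says "Evidence of comorbidities or hospitalization during follow-up will be considered as new diagnoses", and then "Once diagnosed, patients will be considered diagnosed for the remainder of their follow-up". Hospitalization is thus named in the same rule as the comorbidities. Table 5.3 defines it only as "Evidence of inpatient claim(s) Yes, No", with no count and no window.

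The same section gives rolling windows to other covariates: 180 days for ART adherence, and 365 days for the physical exam, influenza vaccine, CD4 test and viral load test.

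Protocol 9.7 lists as time-varying covariates "hospitalization, opportunistic infections, ART adherence, annual CD4 and viral load laboratory tests, and an indicator for respiratory virus season". Opportunistic infections are diagnosis-coded, yes or no, at baseline and in follow-up, with one outcome-specific exception: "In the analysis of all-cause pneumonia, pneumocystis jirovecii pneumonia codes are excluded from the follow-up". Immunosuppressive medication has its own definition ("PLWH will be considered on immunosuppressive medications if" a code or dose-and-duration condition is met), and nothing says when a person stops counting as exposed. Pneumonia is a covariate at baseline only.

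SAP 5.8.4 lags the time-varying covariates by one 30-day interval and builds the censoring weights by the same methods as the treatment weights.

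**The concern.** Admissions and acute infections are episodic. A recent one can shift the chance of being vaccinated, downward if vaccination is deferred or upward if discharge brings contact with care, and it can raise short-term pneumonia risk. That is time-varying confounding of the kind the weights are meant to remove. SAP 5.8.4 justifies time-varying covariates by saying that baseline values can represent later status poorly; a permanent flag brings that problem back for everyone already flagged. The covariates that do have windows mostly describe care-seeking and adherence. No illness covariate has a stated recency window.

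The outcome most exposed is all-cause pneumonia, where the expected VE is small (5% to 15%, Protocol 9.5) and the planned intervals are narrow. A bias of a few points could be read as a vaccine effect, or could hide one.

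**Working it through.** **No plan figure to reproduce.** The point concerns a coding rule. The check asks how quickly the flag loses information, and what that could do to the VE.

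**1. Loss of information.** The documents give no admission rate, so h = 8%, 15% and 25% per year are assumptions. With constant, equal risk, the share ever flagged after the half-year baseline plus t years is 1 − (1 − h)^(0.5 + t). The share of those admitted in the last 12 months is h divided by that.

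| | h = 8% | h = 15% | h = 25% |
|---|---|---|---|
| t = 1: flagged | 12% | 22% | 35% |
| t = 1: of these, admitted in last year | 68% | 69% | 71% |
| t = 5: flagged | 37% | 59% | 79% |
| t = 5: of these, admitted in last year | 22% | 25% | 31% |

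The flag is a fair proxy for recent admission early in follow-up and a poor one late. Unequal risk lowers the five-year flagged shares to 34%, 53% and 71% (log-normal frailty, SD 0.7).

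**2. Effect on VE, simulation A.** 1.5 million people, 60 months, true VE 0, h = 15%, frailty SD 0.7. Admission within 6 months alters pneumonia risk and vaccination by the ratios shown. Entries are spurious VE in points.

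| Pneumonia ratio | Vaccination ratio | Ever flag only | Recent indicator added |
|---|---|---|---|
| 3 | 0.5 | +0.9 | 0.0 |
| 4 | 0.3 | +2.1 | +0.4 |
| not restated | 2 | −1.5 | −0.1 |

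**3. Simulation B.** 400,000 people, 36 intervals of 30 days, true VE 0, log-normal frailty SD 1. Pneumonia incidence (5,487 per 100,000) and uptake (32%, reached over the 36 intervals) are taken from Protocol 9.5. Weights are stabilized, lagged one interval and constant after vaccination. The confounder is admission in the last 90 days. Unless stated, it triples pneumonia risk and halves vaccination.

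| Scenario | Crude | Ever flag | Ever + 90-day flag |
|---|---|---|---|
| 10%/yr, frailty does not affect pneumonia | 0.4 | 0.3 | 0.0 |
| 10%/yr, moderate frailty effect | 1.5 | 0.5 | −0.1 |
| 10%/yr, strong | 3.0 | 0.8 | −0.7 |
| 20%/yr, moderate | 3.0 | 1.4 | 0.0 |
| 20%/yr, strong | 6.0 | 2.8 | −0.4 |
| same, pneumonia ratio 6 | 7.9 | 4.1 | −0.7 |
| same, vaccination ratio 0.25 | 9.5 | 4.9 | 0.3 |
| same, ratios 6 and 0.25 | 12.5 | 7.3 | 0.3 |
| same, heavier-tailed frailty (SD 1.5) | 15.7 | 8.8 | −2.9 |
| same, vaccination ratio 2 | −10.1 | −3.5 | 0.7 |
| same, vaccination ratio 1 | 0.1 | 0.1 | 0.2 |

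The rows marked same start from 20%/yr with a strong frailty effect. Where admission is related to vaccination, the ever flag leaves between 0.8/3.0 = 27% and 0.3/0.4 = 75% of the crude bias. A 365-day flag does little better than the ever flag (2.3 against 2.8 in the 20%/yr, strong row).

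**4. Scale.** Protocol Table 3, VE 5%: 1 to 9 at 36 months, half-width (9 − 1)/2 = 4; 2 to 7 at 97 months with 4% censoring, (7 − 2)/2 = 2.5; 2 to 8 with 10% censoring, 3. For IPD, Table 2 at VE 7.5%, 97 months and 4% censoring gives (19 + 5)/2 = 12, so the same bias matters much less there.

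**The case against.** **The covariate does adjust.** The flag switches on at the first admission and enters the lagged models, removing about 25% to 73% of the crude bias in simulation B. ART adherence, care markers and newly diagnosed comorbidities are also in the weights and may carry some of the same signal; the simulations omit them. This stands. Only recency and repetition are missed.

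**The numbers are assumed and the remedy is favoured.** Each simulated confounder is admission within a chosen window, and the added flag uses that window, so the return to about zero is partly built in. This also stands. The simulations show a mechanism and a plausible size, not the bias in this database.

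**Residual confounding is already anticipated.** Negative controls are planned (SAP 5.8.8 and 5.8.12). They may detect the problem, but correction is optional, and they do not replace adjustment for information already in the claims. The balance checks in 5.8.5 use the listed covariates, so the ever flag could look balanced while recent admission is not.

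**Baseline admissions may be handled separately.** Protocol 9.7 lists hospitalization among both the time-fixed and the time-varying covariates, which could mean two variables. SAP Table 5.3 has one. With two, the follow-up flag would freeze at the first follow-up admission instead; recency and repetition would still be lost.

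**Stronger readings that the documents do not support.**
- That illness is unadjusted and healthy-vaccinee bias therefore remains: the documents do not say whether recent admission delays or prompts vaccination, so the sign is unknown.
- That the bias matches the expected VE of 5% to 15%: only the two most extreme runs exceed 5 points.
- That the permanent rule covers immunosuppressive medication: the rule speaks of diagnoses, comorbidities and hospitalization. For drug courses the SAP is silent.
- That everyone entering by the inpatient route is flagged from index: the criterion ("HIV infection defined as at least one inpatient International Classification of Diseases, Ninth Revision, Clinical Modification (ICD-9-CM" and so on) does not require the first HIV code to be the inpatient one, and the number affected is not given.

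**Conclusion.** The concern holds in a limited form. A stated rule makes hospitalization permanent, so a new admission is invisible to the weight models in anyone already flagged. Opportunistic infections plausibly share the rule because they are diagnosis-coded, though it does not name them. For immunosuppressive medication the defect is a missing off-rule.

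The consequence is a risk of residual confounding of unknown sign. Under assumed rates it is roughly 1 to 3 VE points in moderate scenarios, below 1 at 10% admissions per year, and about −1.5 to −3.5 if admission prompts vaccination. Values of 4 points and above need strong or extreme assumptions. Against a half-width of about 2.5 to 4 points for an all-cause pneumonia VE of 5%, that is enough to matter for this outcome and little for IPD. Apart from the pneumonia incidence and the 32% uptake, every simulation input is an assumption.

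**What to change.** In SAP 5.3.2 and Table 5.3:

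- Keep the permanent rule for chronic comorbidities.
- For hospitalization and opportunistic infections, add a lagged recent-event indicator (for example, previous 90 to 180 days) beside the ever flag in the IPTW and IPCW denominator models. Keep the window short, since 365 days helped little. Keep the existing outcome-specific exclusions for opportunistic infections.
- Define immunosuppressive medication by a similar current-or-recent window, with a stated rule for when exposure ends.
- State whether baseline and follow-up hospitalization are one variable or two.
- Report standardized differences for the recent-window variables in 5.8.5.

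The cost is a few derived variables from claims already held, a few more parameters in the weight models and slightly more variable weights. Truncation at the 1st and 99th percentiles is available in 5.8.4 but optional, so the weight distributions should be reviewed once the variables are added. The window should be fixed before VE results are seen.
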